**Table 5-6 Study drug dispense during open-label treatment epoch**

Dose Level	Visit	Sacubitril/valsartan**	Route	Timing
2 a	Week 12/Visit 6	49/51 mg	Oral	AM & PM
3	Week 14/Visit 7	97/103 mg	Oral	AM & PM

\*\*Investigational product labeling for sacubitril/valsartan dose levels is based on the total contribution of both components of sacubitril/valsartan and reads, 50 mg, 100 mg and 200 mg. This is equivalent to the sacubitril/valsartan dose levels 24/26 mg, 49/51 mg and 97/103 mg, respectively.

- All patients entering the open-label treatment epoch will start open-label treatment on sacubitril/valsartan 49/51 mg BID (Dose Level 2) unless they completed the double-blind treatment epoch on Dose Level 1. Instead, these patients will enter the open-label epoch on sacubitril/valsartan 24/26 mg BID dose (Dose Level 1).
- Study treatment will be force-titrated every 2 weeks to reach the target dose of sacubitril/valsartan 97/103 mg BID (Dose Level 3).

Schedule and dose adjustments will only be allowed if, in the investigator's judgement, the adjustment/elimination of concomitant medications is not possible or does not alleviate the side effects of concern. See [Section 5.5.5](#).

### **5.5.5 Permitted dose adjustments and interruptions of study treatment based on safety and tolerability**

Study drug dose level adjustments should be mainly based on overall safety and tolerability and investigator judgement, with a special focus on:

- hyperkalemia;
- clinically significant decreases in eGFR/increase in serum creatinine; and,
- symptomatic hypotension

**Table 5-7 Safety and tolerability guidance for dose adjustments**

Parameter	Criteria
Potassium level	K > 5.3 mEq/L
Kidney function	
 
• eGFR reduction ≥ 35% compared to baseline; OR, serum creatinine of ≥0.5mg/dl with at least a 25% decrease in eGFR
 

Blood pressure	
 
• No symptomatic hypotension or SBP < 90 mmHg
 

Adverse events (AEs) or conditions	
 
• No postural symptoms or any conditions that preclude continuation according to the investigator's judgment
 

Every attempt should be made to maintain patients on target study drug Dose Level 3 for as long a duration as possible throughout the study. If, however, in the opinion of the investigator, a patient is unable to tolerate the protocol-specified target dose, the investigator will manage the patient's treatment according to the below guidelines:

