##### Double-blind, randomized treatment epoch

- On Day 1 (Visit 2), patients will be randomized to either sacubitril/valsartan 24/26 mg BID or enalapril 2.5 mg BID (Dose Level 1), according to the product label(s) and will return for a safety assessment at Week 1 (Visit 3).
- Study treatment will be force-titrated every 2 weeks to reach the target dose of sacubitril/valsartan 97/103 mg BID and enalapril 10 mg BID (Dose Level 3).

Deviation from the titration schedule or dose adjustments will only be allowed if indicated per protocol defined safety and tolerability criteria (See [Section 5.5.5](#), [Table 5-7](#)) and investigator judgement, if the investigator believes that adjustment/elimination of concomitant medications is not possible or does not alleviate the side effects of concern.

At any time during the 12 week randomized, double-blind treatment epoch, investigators have the option to withdraw patients from study treatment if they develop signs and symptoms of worsening heart failure for which the investigator would like to administer appropriate therapy. (See [Section 5.5.5](#) and [Section 5.5.6](#))

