## **13 Appendix 1: Clinically notable laboratory values and vital signs**

Clinically notable vital signs will be defined in this study as a SBP < 90 mmHg. The study treatment shall be interrupted or stopped based on investigator judgement.

Clinically notable laboratory abnormalities for selected tests based on a percent change from baseline:

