2.8.3 Laboratory data

Laboratory values will be summarized using shift tables (from baseline to most extreme post baseline value) by each laboratory parameter at its worst severity by study phase (see Section 2.1.1 for study phase phase definitions). The number and percentage of patients with laboratory values will be presented by low/normal/high (low and high) classifications to compare baseline to worst post baseline value. Unscheduled assessments will be considered.

In addition, laboratory values and the change from baseline for each parameter by visit will be summarized by treatment group and open-label sacubitril/valsartan. In the event there are multiple laboratory values within a visit, the worst value will be summarized.

A separate summary table will be presented by study phase (see Section 2.2.1 for study phase phase definitions) with the number and percentage of patients having notable lab abnormalities based on percent change from baseline (see Section 5.3 for a list of notable laboratory abnormalities). Unscheduled assessments will be considered.

Listings of all laboratory values will be provided. A separate listing for pregnancy tests will also be provided. Any notable laboratory abnormalities will be flagged.

Laboratory values indicated as $<x$ will be converted to $(0.5)(x)$ for purposes of analysis. Laboratory values indicated as $>x$ will be converted to the values specified in the below table for purposes of analysis.

Laboratory Test	Unconverted Value	Converted Value for Analysis
Red Blood Cell Count	>7.00	7.1
Potassium	>7.0	7.1
Urine Erythrocytes	>182	182.1
Urine Leukocytes	>182	182.1

The incidence of hyperkalemia through Week 12 will be calculated by treatment group. The relative risk (sacubitril/valsartan vs. enalapril) and 95% confidence interval will be presented. Hyperkalemia will be determined from the central laboratory data as potassium >5.3 mEq/L. Unscheduled assessments will be considered.

Similarly, the incidence of worsening renal function through Week 12, relative risk (sacubitril/valsartan vs. enalapril) and 95% confidence interval will be presented. Worsening renal function will be determined from the central laboratory data as a worsening (decrease) in eGFR of $\geq 35\%$ from baseline, or an increase in creatinine of ≥ 0.5 mg/dL from baseline and a worsening (decrease) in eGFR of $\geq 25\%$ from baseline. Unscheduled assessments will be considered.

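### Table 5-7 states creatinine as a level instead of a rise from baseline, so its renal criterion collapses to a 25% eGFR fall; two other rows are worded in reverse

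*Protocol*

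**What the plan says.** Protocol 3.1 makes the table the reference for dosing: "Deviation from the titration schedule or dose adjustments will only be allowed if indicated per protocol defined safety and tolerability criteria", citing Section 5.5.5 and Table 5-7 together with investigator judgement. The same sentence appears for the double-blind and the open-label epochs.

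The kidney row of Table 5-7 has two limbs. The first is an eGFR reduction of at least 35% from baseline. The second reads "OR, serum creatinine of ≥0.5mg/dl with at least a 25% decrease in eGFR". The text introducing the table names "clinically significant decreases in eGFR/increase in serum creatinine" as a point of focus, without giving a size.

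SAP 2.8.3 defines worsening renal function as an eGFR fall of at least 35% from baseline, "or an increase in creatinine of" at least 0.5 "mg/dL from baseline and a worsening (decrease) in eGFR of" at least 25%.

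The other rows of Table 5-7 are potassium above 5.3 mEq/L; "No symptomatic hypotension or SBP" below 90 mmHg; and "No postural symptoms or any conditions that preclude continuation", as the investigator judges.

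**The concern.** The table and the SAP share the 35%, 0.5 mg/dL and 25% figures, but the table has lost the words that make 0.5 mg/dL a rise over baseline. A creatinine level of 0.5 mg/dL does not indicate renal impairment. Joined to a 25% eGFR fall, it adds no restriction, and it makes the 35% limb in the same row pointless.

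The design depends on patients reaching and holding Dose Level 3. A site that followed the row as printed could reduce the dose for a smaller renal change than intended, mainly in patients with better baseline function. The SAP reports renal dysfunction as a reason for not reaching Dose Level 3 (2.3.1) and separately reports worsening renal function (2.8.3). If the dosing table works at 25% and the reported definition at up to 35%, those two outputs are harder to reconcile.

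Separately, two rows point the opposite way from the other two under one column heading. Read literally, a patient without hypotension would meet a criterion for dose adjustment.

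**Working it through.** The plan gives no figure of its own to reproduce here, so the check compares the two rules algebraically.

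**Inputs.** The thresholds 35%, 25% and 0.5 mg/dL come from Table 5-7 and SAP 2.8.3. Protocol 4.2 (exclusion 9) names the MDRD formula but gives no coefficients. I therefore assume eGFR is proportional to creatinine^-k with k = 1.154, and show the range k = 1.0 to 1.2. Baseline creatinine values b are illustrative.

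**Step 1: does the printed creatinine condition ever bind?** A 25% eGFR fall multiplies creatinine by (4/3)^(1/k) = 1.283. The result is below 0.5 mg/dL only if b < 0.5/1.283 = 0.39 mg/dL (0.375 at k = 1.0; 0.393 at k = 1.2). For any realistic adult baseline the printed row is simply an eGFR fall of at least 25%.

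**Step 2: the intended rule.** A rise of 0.5 mg/dL gives an eGFR fall of 1 - (1 + 0.5/b)^-k. At k = 1.154 this is 37.4%, 33.1%, 28.3% and 22.7% for b = 1.0, 1.2, 1.5 and 2.0. The intended trigger is min(35%, max(25%, that fall)).

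| Baseline creatinine (mg/dL) | Printed trigger | Intended trigger, k = 1.154 (k = 1.0; 1.2) | Gap in percentage points (k = 1.0; 1.2) |
|---|---|---|---|
| 1.0 | 25% | 35.0% (33.3; 35.0) | 10.0 (8.3; 10.0) |
| 1.2 | 25% | 33.1% (29.4; 34.2) | 8.1 (4.4; 9.2) |
| 1.5 | 25% | 28.3% (25.0; 29.2) | 3.3 (0; 4.2) |
| 2.0 | 25% | 25.0% (25.0; 25.0) | 0 (0; 0) |

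**Step 3: where the gap starts and ends.** The full 10 points apply when b ≤ 0.5/((1/0.65)^(1/k) - 1) = 0.5/0.4525 = 1.10 mg/dL (0.93; 1.16). The gap is zero when b ≥ 0.5/((4/3)^(1/k) - 1) = 0.5/0.2831 = 1.77 mg/dL (1.50; 1.85). The maximum, 35 - 25 = 10, does not depend on k.

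**Step 4: in creatinine terms.** The printed row is met at a rise of b × 0.283: 0.28 mg/dL at b = 1.0 (0.33; 0.27), 0.34 at 1.2 (0.40; 0.33) and 0.42 at 1.5 (0.50; 0.41). The intended rule is met at 0.45 (0.50; 0.43), 0.50 and 0.50 mg/dL.

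**Step 5: evidence of intent.** The lead-in to the table speaks of an increase in creatinine. Two other SAP safety definitions agree with Table 5-7's thresholds: potassium above 5.3 mEq/L (2.8.3) and systolic pressure below 90 mmHg (2.8.4.1). Of these three measured parameters, only the renal one differs.

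**Step 6: the reversed rows.** Appendix 1 treats systolic pressure below 90 mmHg as notable and adds: "The study treatment shall be interrupted or stopped based on investigator judgement". Appendix 3 has the study drug reduced or temporarily withdrawn when hypotension persists. Both treat hypotension as the reason to act, whereas the table row is worded as its absence.

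**The case against.** The strongest reply is that no competent investigator would be misled. The sentence above the table mentions a creatinine increase, a level of 0.5 mg/dL is plainly not a warning sign, and the redundant 35% limb shows that the literal reading cannot be right. The table is titled guidance, Section 5.5.5 rests on investigator judgement, and concomitant drugs are to be adjusted first, so meeting the row does not by itself cause a dose reduction. The SAP rule defines a safety summary and is not a dosing rule; nothing requires the two to match. Appendix 4 already asks for review at a 25% eGFR fall and lists study medication among the causes to check. The 10 points are a ceiling, and nobody would cut a dose because hypotension is absent.

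Most of this stands, and it limits the weight of the point. It does not make the printed threshold right. Section 3.1 cites this table as the criteria for departing from forced titration, and Appendix 4 at 25% calls for a check, not a dose change. The SAP serves here as evidence of what the table was meant to say. That a reader can work out the intended rule is a reason to grade the error as minor, but it still needs correcting.

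**Conclusion.** The point holds, as a minor inconsistency. The printed renal criterion is in practice a 25% eGFR fall at any baseline creatinine above about 0.39 mg/dL. The intended trigger lies between 25% and 35% depending on baseline, so the printed row is up to 10 percentage points too permissive and is correct only from about 1.77 mg/dL upward. Two of the four rows are worded in the wrong direction.

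The crossover baselines rest on the assumed exponent; the 10-point maximum and the conclusion do not. The number of extra dose adjustments cannot be estimated, because the documents give no distribution of baseline creatinine or of eGFR change. Both blinded arms use the same table. The primary analysis, type I error, power and the SAP's safety incidence definitions are unaffected.

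**What to change.** Reword the second renal limb of Table 5-7 as a rise in serum creatinine of at least 0.5 mg/dL over baseline together with an eGFR fall of at least 25% from baseline, in line with SAP 2.8.3. Remove the leading negative from the blood pressure and adverse event rows so that all four rows state triggers. The cost is three reworded rows and a notice to sites, with no new procedures, patients or analyses. If dosing has finished, a clarifying note in the study report would be enough.

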**1. Adjust Concomitant Medications**

- Dose adjustments/elimination of concomitant medications may remedy the situation before reducing the dose of study treatment. If adjustment of the concomitant medications is not possible or does not alleviate the side effects of concern, THEN;

**2. Adjust Study Treatment Dose Level**

- Down-titrate study treatment to the previous dose level. The patient may continue receiving the lower dose level for a recommended period of 1 to a maximum of 4 weeks.
- A re-challenge to titrate back up to the target dose level should be attempted at 2 weeks, or when patient is deemed stable. THEN:

**3. Further Adjust Study Treatment Dose Level**

- If tolerability issues are not alleviated despite down-titration by one dose level, the investigator may down-titrate further to the next lower study treatment dose level. The patient may continue receiving the lower dose level for a recommended period of one to a maximum of 4 weeks, up to a temporary withdrawal of study treatment. See Step 5.
- Again, once stable, the patient should be re-challenged with up-titration to the next higher dose level in an attempt to gradually bring the patient back to the target study treatment dose level (Dose Level 3).
- The investigator may choose the next dose level for down- or up-titration according to his or her clinical judgment.

**4. Stopping Study Treatment**

If needed, the study treatment may be stopped completely, however, the patient should continue to attend all study visits and be followed until the completion of the study. See [Section 5.5.6](#).

## 5. Study drug restart after temporary treatment interruption

- Once the investigator considers the patient's condition appropriate for receiving the study drug, the investigator should re-start the patient on study treatment at the most appropriate and allowable dose level per his/her medical judgment.
- If tolerated, the patient should be titrated up to the next dose level every 1 to 4 weeks, as per the investigator's judgment.
- In some instances, Dose Level 1 or 2 could be maintained if the investigator considers that the patient's condition would not allow any further up-titration to the target dose of study medication (Dose Level 3). In this case, it would be acceptable to maintain the patient at Dose Level 1 or 2, whichever is the higher and tolerated dose level by the patient, but reasons for not getting to Dose Level 3 need to be captured in the eCRF.
- Should the patient not tolerate the re-start study drug dose level, he/she may be down-titrated again (if appropriate) or discontinued from study treatment.

Patients re-started on the study drug will retain their original randomization and study identification numbers.

The IRT must be contacted to register any changes in the patient's study treatment dose level, including in cases of temporary and permanent withdrawal or re-start of the study drug, and to obtain the medication numbers of the study drug supplies required for the new study treatment dose level. All dose changes and interruptions must also be recorded on the Dosage Administration Record eCRF.

Study visits should occur as close as possible to the pre-defined visit and time schedule described in [Table 6-1](#). The timeframe between the regular visits should be maintained as scheduled, irrespective of the number of unscheduled visits that may be performed in between, or dose interruptions that may occur.

In case of pregnancy discovered during the study, the patient should be instructed to stop taking the study drug immediately. (See [Section 6.5.6](#) and [Section 7.6](#))

### 5.5.6 Rescue medication for worsening heart failure

At any time during the 12 week randomized, double-blind treatment epoch, investigators have the option to withdraw patients from study treatment if they develop signs and symptoms of worsening heart failure for which the investigator would like to administer appropriate therapy.

- Appropriate adjustments, intensifications, or additions to concomitant medications should be considered before deciding to withdraw the patient from study treatment.
- **Other than their study treatment, patients CANNOT receive ACEis, ARBs, or sacubitril/valsartan during the study. These medications can ONLY be administered if the investigator believes that the patient needs to be withdrawn from study treatment so that they may be treated with these therapies due to signs and symptoms of worsening heart failure.**
- **A 36 hour wash-out period is required if the investigator chooses to withdraw the patient from double-blind treatment and switch to sacubitril/valsartan or ACEi due to symptoms of worsening heart failure.**

- Use of rescue medication must be recorded on the Concomitant medications eCRF.

Investigators will use clinical judgement to determine if patient condition requires closer monitoring. Unscheduled visits are permitted as needed.

Guidance on handling hyperkalemia, hypotension, and renal dysfunction are provided to investigators in the appendices.

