### **3.4 Rationale for choice of comparator**

Treatment with ACEi has been well established as the standard of care for RAAS blockade and is recommended by treatment guidelines as a 1A recommendation for all patients with CHF and reduced LVEF, unless ACEi-intolerant. Additionally, ACEi may reduce aortic stiffness by opposing vasoconstrictive, hypertrophic, and profibrotic effects of angiotensin II on the vessel wall.

As a well-studied ACEi in heart failure, enalapril has been selected as the comparator for this study with a target dose of 10 mg BID. The 10 mg BID dose was the same target dosage studied in the SOLVD study and is the dose that was chosen in the PARADIGM-HF trial. The same dose will be used in this study so that we can appropriately assess the hemodynamic benefits of the drug and whether it supports the clinical outcomes that were seen in both trials.

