In the PARADIGM-HF study, sacubitril/valsartan reduced the risk of CV death and HF hospitalization versus enalapril. In the US, sacubitril/valsartan is approved and indicated to reduce these risks in patients with chronic heart failure (NYHA class II-IV) and reduced ejection fraction. Due to this, the double-blind treatment epoch is limited to 12 weeks to minimize the chance of exposure to standard treatment with enalapril. Thereafter, all patients will have the opportunity to receive 12 weeks of open-label sacubitril/valsartan. It should be noted that the population of patients studied in PARADIGM-HF included NYHA class II-IV patients that were all on either ACEi or ARBs prior to study enrollment. The population of patients included in this study is different than that of PARADIGM-HF.

There is a chance a patient may develop signs and symptoms of worsening heart failure for which the investigator would like to administer appropriate therapy. Appropriate adjustments, intensifications, or additions to concomitant medications should be considered. If needed, the investigator can choose to withdraw the patient from the study to initiate treatment with sacubitril/valsartan, ACEi, or ARBs if the investigator believes this to be appropriate treatment. Rescue options are provided in [Section 5.5.6](#).

In addition to investigational treatment, all patients will be allowed to continue receiving the rest of their background cardiovascular (CV) medications throughout the study. Patients will be randomized to study treatment only after the investigator has confirmed the patient is on stable treatment with guideline-directed therapy for HFrEF, other than ACEis and ARBs, which will ensure that patients are receiving appropriate treatment for their heart failure.

The study procedures and assessments for this study are either non-invasive or minimally invasive (venipuncture for blood draws) and are considered low risk.

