### **5.5.3.3 Handling of non-study treatment**

The following non-study treatment has to be monitored specifically and recorded in the CRF:

- ACEi/ARB treatment prior to randomization and/or after early discontinuation of study treatment.
- All protocol required background therapy.
- Rescue treatment.

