#### ACEis and ARBs:

Patients taking an ACEi at screening must undergo a 36-hour washout prior to randomization (Visit 2). Patients taking an ARB must discontinue the ARB prior to initiating treatment with study medication however, a washout is not necessary.

The concomitant use of ACEis or ARBs is strictly prohibited while the patient is receiving study medication. Adjustment, intensification, or addition of concomitant medications should be considered first before the decision is made to treat the patient with an ACEi or ARB. **If the investigator believes that the patient needs to be withdrawn from the study medication so that they may be treated with either an ACEi or ARB, the study medication must first be stopped and a 36-hour washout period will be required for patients being switched to an ACEi.**

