**Table 5-9 Prohibited medication**

Medication	Prohibition period	Action taken
ACEis/ARBs/NEPs	ACEi 36 hour prior to study treatment, ACEi, ARB, NEP during study treatment, ACEi and NEP within 36 hours post double-blind randomization.	If the investigator believes that addition of an ACEi ARB or sacubitril/valsartan is necessary, then study drug must be discontinued, while monitoring renal function. ACEi or sacubitril/valsartan must not be started until 36 hours after discontinuing study drug to reduce the risk of angioedema.
Renin inhibitors (Aliskerin)	During study treatment.	Do not randomize, or, use alternate treatment.
Bile acid sequestering agents (such as cholestyramine or colestipol)	During study treatment.	Switch to alternate agent to avoid interference with study drug absorption. If use of alternate agent is not allowed, do not randomize or discontinue study drug treatment.
Nesiritide and intravenous nitrates	During study treatment.	Do not randomize. If hospitalized, either interrupt or discontinue study treatment. Nesiritide and intravenous nitrates have not been studied. Oral, topical and sublingual nitrates are permissible.

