### **5.6.2 Discontinuation of study treatment**

Discontinuation of study treatment for a patient occurs when study drug is stopped earlier than the protocol planned duration, and can be initiated by either the patient or the investigator.

The investigator must discontinue study treatment for a given patient if, on balance, he/she believes that continuation would negatively impact the risk/benefit of trial participation.

Patients may voluntarily discontinue the study drug for any reason at any time.

Study treatment must be discontinued under the following circumstances:

- Patient wish
- Withdrawal of consent
- Pregnancy (see [Section 6.5.8](#) and [Section 7.6](#))
- Use of prohibited treatment as per recommendations in [Table 5-9](#)
- Any protocol deviation that constitutes a risk to the patient

- Any situation in which study participation might result in a safety risk to the patient
- Unresolved worsening HF

Study medication may be discontinued at the investigator's discretion if any of the following serious suspected drug-related AEs occur:

- Symptomatic hypotension
- Suspected occurrence of angioedema. A patient with any signs or symptoms of clinically significant angioedema should be thoroughly evaluated by the investigator to determine if it constitutes a reason for discontinuation of study medication.
- Any laboratory abnormalities that in the judgment of the investigator, taking into consideration the subject's overall status, prevents the subject from continuing participation in the study.

Depending on the serum potassium, blood pressure, or eGFR, patients may need to have their study drug dose or the dose of another concomitant medication reduced or discontinued; or, if appropriate, have potentially contributing agents adjusted. Refer to appendices for treatment guidelines for hyperkalemia, hypotension or renal dysfunction, respectively.

If discontinuation of study treatment occurs, the patient should NOT be considered withdrawn from the study. The investigator must determine the primary reason for the patient's premature discontinuation of study treatment and record this information on End of Study Treatment eCRF. After study treatment discontinuation, the patient should attend the regularly scheduled visits and have all study assessments performed.

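### Protocol Section 5.5.6 and the lead sentence of 5.5.8 conflict with Section 5.5.7 and Table 5-9 on ACEi, ARB or sacubitril/valsartan use after study drug is stopped, and Section 3.6.1 conflicts with 5.5.6 and 5.6.2 on whether a rescued patient stays in the study

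*Protocol*

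**What the plan says.** Four places in the protocol govern non-study ACEi, ARB or sacubitril/valsartan after randomization.

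- Section 5.5.6, on rescue for worsening heart failure, says that, apart from study treatment, "patients CANNOT receive ACEis, ARBs, or sacubitril/valsartan during the study. These medications can ONLY be administered if the investigator believes" the patient needs to come off study treatment so that worsening heart failure can be treated with these drugs. That is its one exception.
- Section 5.5.7, for ACEi and ARB: "The concomitant use of ACEis or ARBs is strictly prohibited while the patient is receiving study medication". A switch rests on the investigator's belief that it is needed, after study drug is stopped (with a 36-hour washout for an ACEi). Worsening heart failure is not a condition.
- The lead sentence of Section 5.5.8 bars the listed drugs at any time after screening.
- Table 5-9, directly below it, gives the prohibition period as the time on study treatment plus 36-hour windows, and adds: "If the investigator believes that addition of an ACEi ARB or sacubitril/valsartan is necessary, then study drug must be discontinued". This covers all three drugs, again with no heart-failure condition.

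On follow-up status, Section 5.6.2 says: "If discontinuation of study treatment occurs, the patient should NOT be considered withdrawn from the study". It asks that such patients attend the regular visits and have all assessments. Its reasons for stopping include patient wish, symptomatic hypotension, suspected angioedema and laboratory abnormalities, as well as unresolved worsening heart failure. Step 4 of Section 5.5.5 likewise keeps patients who stop study drug on all visits, and then refers to Section 5.5.6.

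Section 3.6.1, discussing worsening heart failure, says "the investigator can choose to withdraw the patient from the study to initiate treatment with sacubitril/valsartan, ACEi, or ARBs". Sections 3.1 and 5.5.6 describe the same act as withdrawal from study treatment.

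**The concern.** Two questions that a site will face have more than one answer in the current text.

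The first is what a patient may receive after permanently stopping study drug for a reason other than worsening heart failure while staying in follow-up. Sites working from different sections would manage the same patient differently. The primary analysis uses the Full Analysis Set by assigned arm, and off-drug patients are meant to have Week 12 tonometry. What those patients take after stopping is therefore part of what the Week 12 comparison measures, and at present it depends on which section the site read.

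The second is whether a rescued patient is still in the study. If the site follows Section 3.6.1, the patient leaves and the scheduled Week 12 Zc may never be obtained. SAP Section 2.5.3 does not impute a missing Week 12 value and removes the patient from the primary analysis. That loss would be tied to clinical worsening, and it would affect data that Section 5.6.2 intends to keep.

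**Working it through.** No figure in the plan enters this point, so the check is a side-by-side reading.

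| Protocol text | When the drugs are barred | Condition for using them |
|---|---|---|
| 5.5.6 | Throughout the study | Only withdrawal from study treatment for worsening heart failure |
| 5.5.8, lead sentence | Any time after screening | None stated |
| 5.5.7 (ACEi/ARB) | While on study medication | Investigator judgement; study drug stopped first |
| Table 5-9 (all three) | During study treatment, plus 36-hour windows | Investigator judges it necessary; study drug discontinued |

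Both columns differ, so this is a difference in rule and not only in phrasing. Section 5.5.8 also disagrees with its own table.

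Now follow one patient who permanently stops study drug before Week 12 because of symptomatic hypotension.

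1. Section 5.6.2 allows the stop, keeps the patient in the study and asks for all assessments.
2. Section 5.5.5 step 4, which deals with tolerability, also keeps the patient on all visits and points to Section 5.5.6.
3. Under Section 5.5.6 as worded, the patient is still in the study and the stop was not for worsening heart failure, so the drugs are not allowed. The lead sentence of 5.5.8 agrees.
4. Under Section 5.5.7 the patient is no longer receiving study medication, so an ACEi or ARB is not barred. Table 5-9 gives the same answer for all three drugs once study drug is stopped, subject to the 36-hour interval for ACEi and sacubitril/valsartan.

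Steps 3 and 4 cannot both be followed.

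Next, a patient rescued for worsening heart failure.

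1. Section 3.6.1: withdrawn from the study to start these drugs.
2. Sections 3.1 and 5.5.6: withdrawn from study treatment.
3. Section 5.6.2: stopping study treatment is not study withdrawal, and scheduled assessments continue.
4. SAP Section 2.5.3: with no Week 12 value, the patient is out of the primary analysis.

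Step 1 conflicts with steps 2 and 3. Step 4 shows where the difference reaches the primary result.

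**The case against.** The strongest reply is context. Section 5.5.6 has a rescue heading, opens with the 12-week double-blind epoch, and its ban begins by setting study treatment aside, which presupposes a patient still taking it. On that reading it only says when an on-drug patient may be switched, and Section 5.5.7 and Table 5-9 cover everyone already off drug. This is a reasonable guess at the intent, and the problem may be no more than loose drafting. It does not remove the conflict. The words used are study-wide with a single exception, the lead sentence of 5.5.8 is equally broad, and a tolerability step outside the rescue section sends off-drug patients to 5.5.6.

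On follow-up status, Section 3.6.1 is one phrase in a risk narrative that itself defers to 5.5.6, and the operative sections agree with each other. That limits the problem but does not cancel the instruction.

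Data loss is also partly covered. Section 6 and Table 6-1 ask for Visit 6 assessments when a patient leaves the double-blind period early. SAP Section 2.5.4 adds last-observation-carried-forward and repeated-measures analyses, and the sample size allows for 20% dropout and 10% non-evaluable data. These soften the effect. An exit assessment is still not the scheduled Week 12 value, and the two extra analyses are supportive only.

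Several stronger readings are tempting and are not supported:

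- A reader might infer that patients who stop for other reasons are pushed out of the study. No passage does this. Section 5.6.2 makes use of prohibited treatment a reason to stop study treatment, not to leave the study.
- A reader might size the group from the planned dropout, 432 × 0.20 = 86 patients. Section 9.8 defines that rate as dropout from follow-up, whereas the patients at issue remain in follow-up.
- A reader might infer more stopping on sacubitril/valsartan from the hypotension rates in Section 3.6.1 (17.61% versus 11.97% on enalapril). The same section gives renal dysfunction of 10.14% versus 11.52% and hyperkalemia of 11.61% versus 14%, both higher on enalapril. These are event rates, not stopping rates, from a trial population that the protocol calls different.
- A reader might count Section 5.5.3.3 as a further contradiction, since it records "ACEi/ARB treatment prior to randomization and/or after early discontinuation of study treatment". It is a recording rule and can coexist with 5.5.6.
- A reader might take Section 3.4, where ACEi treatment is "recommended by treatment guidelines as a 1A recommendation for all patients with CHF and reduced LVEF, unless ACEi-intolerant", as showing which rule is right. It carries its own exception for intolerance and does not settle what applies to patients who stop for tolerability.

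**Conclusion.** The wording conflict is certain. Sections 5.5.6 and 5.5.8 (lead sentence) against 5.5.7 and Table 5-9 give opposite answers for a patient who is off study drug for a reason other than worsening heart failure and still in follow-up. Section 3.6.1 against 3.1, 5.5.6 and 5.6.2 gives opposite answers on whether a rescued patient remains in the study.

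The consequences are possible, not established. They assume that at least some sites act on the literal text of 5.5.6 or 3.6.1. The size cannot be computed: the documents give neither a rate of stopping study drug while staying in follow-up nor a rescue rate, and nothing in them shows that the effect would differ by arm. The point deserves correction because it bears on patient management and on the completeness and meaning of the Week 12 Zc data, and because the remedy is cheap.

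**What to change.** Reconcile Sections 3.6.1, 5.5.5 step 4, 5.5.6, 5.5.7, 5.5.8 (lead sentence) and Table 5-9 into one statement, placed once and cross-referenced from the others, that sets out:

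(a) what applies to ACEi, ARB and sacubitril/valsartan in a patient who has permanently stopped study drug for a reason other than worsening heart failure and remains in follow-up; and

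(b) the follow-up status of a patient rescued for worsening heart failure, stated consistently with the continued-assessment rule in Section 5.6.2.

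Which clinical rule applies is for the sponsor's clinicians to decide. The request here is only that the document give one answer. The cost is protocol wording, through the amendment route in Section 11.1, and a notice to sites. No visits, tests or patients are added.
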